9.1.2. Pharmacodynamical parameters

Based on the obtained concentrations of C-reactive protein, IL-6 and soluble IL-6 receptor in the blood of each volunteer, the following pharmacodynamic parameters will be calculated at the Protocol-specified time intervals:

1. C_{\max} – maximum blood concentration of C-reactive protein, IL-6 and soluble IL-6 receptor over the observation period.
2. t_{\max} – time to maximum blood concentration (C_{\max}) of C-reactive protein, IL-6 and soluble IL-6 receptor.
3. AUC_{0-1680} – the area under the concentration-time curve for C-reactive protein, IL-6 and soluble IL-6 receptor over the time interval from 0 to 1680 hours. AUC_{0-1680} is calculated using the trapezoidal method with the following formula:

$$AUC_{0-1680} = \sum_{p=2}^{16} \frac{(C_p + C_{p-1}) * (t_p - t_{p-1})}{2},$$

where C_p concentration of C – reactive protein, IL – 6 and soluble IL
– 6 receptor values

ИЛ6 in the blood at t moment of time t_p (hours),

$$t_p \in \{0; 2; 8; 12; 24; 48; 72; 96; 120; 168; 240; 336; 504; 672; 1176; 1680\}_{p=1, \dots, 16}$$

4. C_{\min} – minimum blood concentration of C-reactive protein, IL-6 and soluble IL-6 receptor over the observation period.
5. t_{\min} – time to minimum blood concentration (C_{\min}) of C-reactive protein, IL-6 and soluble IL-6 receptor.

9.2 Statistical analysis methods

The study results will be analyzed using the two-sided statistical hypotheses with a significance level of 0.05.

Translated from Russian to English, dated 06-Jul-2020

Quantitative and scale data

To describe quantitative and scale variables, it is planned to use the following characteristics: mean, median, standard deviation, quartiles, minimum and maximum, and coefficient of variance.

The statistical analysis of the obtained data will be conducted using SAS 10.0 software and the R programming language for statistical data processing. Mann-Whitney, Wilcoxon, Kruskal-Wallis, and Friedman tests will be used to compare quantitative and scaled data. The categorical data will be processed using the Fisher's exact test and the χ^2 Pearson test.

Quantitative data include the following parameters:

- Membrane receptor occupancy with BCD-089

Pharmacokinetics:

- Anti-human interleukin-6 receptor monoclonal antibody concentration
- Area under the curve
- Time (including time to maximum concentration, half-life period)
- Elimination characteristics (clearance, elimination constant)

Pharmacodynamics:

- Human IIL-6, C-Reactive Protein, soluble IL-6 receptor concentrations
- Area under the curve
- Time (including time to maximum concentration, trough concentration, time to achieve trough concentration)
- Elimination characteristics (clearance, elimination constant)

Tenderness:

Value specified in Visual Analogue Scale (out of 10 points)

Safety:

- Complete blood count parameters
- Blood biochemistry parameters
- ECG parameters
- Urinalysis parameters

Translated from Russian to English, dated 06-Jul-2020

- Blood pressure, wrist pulse rate and body temperature
- Size of an abnormal lesion at the injection site reactions
- Time of presence of the abnormal lesion at the injection site

Categorical data include the following parameters:

Pharmacodynamics:

- Proportion of samples showing the maximum signal for membrane IL-6 receptor occupancy

Safety:

- Nature of an abnormal lesion at the injection site
- Frequency of AEs and SAEs by severity grades
- Frequency of grade 3/4 toxicity events
- Frequency of injection-site reactions (total and depending on the type of the lesion)
- Proportion of subjects who developed any grade neutropenia in each cohort.
- Frequency of cases of premature discontinuation from the study due to an AE/SAE

During the analysis, the list of methods used may be extended, if necessary for a high-quality data processing.

9.2. Rationale for the study sample size, including reasoning or calculations to support the statistical power and clinical validity of the study

The calculation of the study sample size was based on the "3 + 3" design and dose levels used in the study.

Volunteers cohort	Dose, mg/kg	Number of mandatory included volunteers	Number of volunteers that can be included in case of DLT development
01	0.06	1	0
02	0.3	3	3
03	0.625	3	3

Translated from Russian to English, dated 06-Jul-2020

Volunteers cohort	Dose, mg/kg	Number of mandatory included volunteers	Number of volunteers that can be included in case of DLT development
04	1.0	3	3
05	1.6	3	3
06	2.2	3	3
07	2.9	3	3

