8. SAFETY ASSESSMENT

List of safety parameters

To assess the safety of the study therapy, the following parameters (secondary endpoints) will be used:

- ✓ Proportion of subjects who developed SAEs in each cohort.
- ✓ Proportion of subjects who developed AEs in each cohort.
- ✓ Proportion of subjects who developed injection site reactions in each cohort.
- ✓ Proportion of subjects who developed grade 3-4 AEs in each cohort.
- ✓ Proportion of subjects who developed any grade neutropenia in each cohort.
- ✓ Proportion of subjects who discontinued the study due to AEs and SAEs in each cohort.

Translated from Russian to English, dated 06-Jul-2020

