9.6. Procedures for reporting any deviations from the initial statistical plan

If the initial clinical study plan must be changed, modifications will be described and explained in the protocol amendment or Interim/Final clinical study report.

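### Section 9.2 names only between-cohort tests that ignore dose order; a prespecified trend test and power-model slope would use the six increasing doses better, at almost no cost (low priority)

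*Combined protocol and SAP*

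**What the plan says.** Section 9.2 (Statistical analysis methods) sets the analysis as "using the two-sided statistical hypotheses with a significance level of 0.05". For quantitative data, "Mann-Whitney, Wilcoxon, Kruskal-Wallis, and Friedman tests will be used to compare quantitative and scaled data". For the rest, "The categorical data will be processed using the Fisher's exact test" and the Pearson chi-square test; the categorical list includes "Proportion of subjects who developed any grade neutropenia in each cohort". The section ends by allowing that "the list of methods used may be extended, if necessary for a high-quality data processing", and section 9.6 adds that "modifications will be described and explained in the protocol amendment or Interim/Final clinical study report".

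The second section numbered 9.2 (sample size rationale) states that "The calculation of the study sample size was based on the '3 + 3' design and dose levels used in the study". Its table gives 1 volunteer at 0.06 mg/kg and 3 mandatory volunteers, plus up to 3 more after a DLT, at each of 0.3, 0.625, 1.0, 1.6, 2.2 and 2.9 mg/kg.

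The readable text names no trend test, dose-response model or dose-proportionality estimate. It does not say which cohorts will be compared, or whether the rank tests will be exact or large-sample.

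**The concern.** Of the named tests, Mann-Whitney, Kruskal-Wallis, Fisher and Pearson can compare independent cohorts. All four give the same p-value if the dose labels are shuffled among cohorts. Friedman, and Wilcoxon if the signed-rank test is meant, work within subjects. In a dose-escalation study with 3 volunteers per level, dose order is the main structure in the data, and a test that discards it spreads 18 volunteers over 5 degrees of freedom.

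At stake is how the final report reads dose-response for PK, PD and safety. A gradual rise may be reported as no difference between cohorts. For AUC and Cmax, a significant Kruskal-Wallis result says only that cohorts differ, not how exposure scales with dose.

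**Working it through.** **Plan's own figure.** Maximum N = 1 + 6 × (3 + 3) = 37, as stated. With no DLT, N = 1 + 6 × 3 = 19, of whom 18 are in cohorts 02 to 07.

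**Inputs.** From the documents: the six doses, n = 3 each, two-sided 0.05. Assumed, because the documents give none: log-normal data with CV 30 to 60%, slopes on log dose, and event risks. A slope of 0.3 over the dose range 2.9/0.3 = 9.67-fold is a rise of 9.67^0.3 = 1.98, about two-fold.

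**Quantitative outcomes: tests compared.** σ² = ln(1 + CV²). Kruskal-Wallis and Jonckheere-Terpstra were simulated with permutation critical values (true size 4.9% and 4.4%). The power model is ln(parameter) = a + b ln(dose), with Sxx = 10.73. Its slope power comes from the noncentral t distribution with 16 df and noncentrality b√Sxx/σ. The 90% CI half-width is t(0.95, 16) × σ/√Sxx.

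Worked at CV 40%: σ = √ln 1.16 = 0.385. Noncentrality = 0.3 × 3.276/0.385 = 2.55, giving 67% power. Half-width = 1.746 × 0.385/3.276 = 0.205.

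| Slope 0.3, 6 × 3 | CV 30% | 40% | 50% | 60% |
|---|---|---|---|---|
| Kruskal-Wallis, permutation | 48% | 29% | 20% | 15% |
| Jonckheere-Terpstra | 82% | 59% | 43% | 32–33% |
| Power-model slope test | 88% | 67% | 50% | 38% |
| Slope 90% CI half-width | 0.16 | 0.21 | 0.25 | 0.30 |

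Power ratios to Kruskal-Wallis are 1.7 to 2.1 for Jonckheere-Terpstra and 1.8 to 2.5 for the power model. Over slopes 0.2 to 0.4 and CV 30 to 60%, 11 of 12 scenarios lie at about 1.7 to 2.5. The exception is slope 0.4 at CV 30%, where Kruskal-Wallis already has 75% and the ratio is 1.3.

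**Binary outcomes.** All 4^6 = 4,096 tables were enumerated, with risk logistic in log dose and the exact trend test scored on log dose. The largest true size under a common risk is 4.8% (trend), 4.5% (Pearson) and 2.1% (Fisher), so the gain is not bought with type I error.

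| Risk, lowest to highest dose | Exact trend | Pearson | Fisher |
|---|---|---|---|
| 5% to 20% | 4.7% | 5.6% | 0.9% |
| 5% to 30% | 9.7% | 7.5% | 2.1% |
| 5% to 50% | 27% | 13% | 5% |
| 5% to 70% | 55% | 22% | 13% |
| 5% to 90% | 86% | 42% | 36% |

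The ratios to Pearson in the last three rows are 27/13 = 2.1, 55/22 = 2.5 and 86/42 = 2.0. As an example, cases 0, 0, 0, 1, 1, 2 by rising dose give p = 0.032 (trend), 0.27 (Pearson) and 0.60 (Fisher).

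**Miss rates.** At slope 0.3, Kruskal-Wallis against Jonckheere-Terpstra runs from 52/18 = 2.9 (CV 30%) down to 85/68 = 1.3 (CV 60%). Against the power model it runs from about 4.4 (unrounded) down to 85/62 = 1.4. Pearson against trend gives 87/73 = 1.2, 78/45 = 1.7 and 58/14 = 4.1. The range is about 1.2 to 4.4.

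**Where the gain shrinks or reverses.**
- Dose-proportional AUC (slope 1, CV 50%): permutation Kruskal-Wallis already has 99%.
- Two-fold step after the lowest dose, then plateau: Jonckheere-Terpstra has about 0.85 to 1.0 times the power of Kruskal-Wallis. Binary risk 5% then 90%: trend 76%, Pearson 78%.
- Risk 5% in five cohorts and 90% at the top dose: trend 68%, Pearson 82%.
- Rise and fall (risk 5, 30, 70, 70, 30, 5%): trend 0.4%, Pearson 34%.
- All cohorts expanded to 6, slope 0.3: ratios fall to 1.1–1.7 (Jonckheere-Terpstra) and 1.1–1.9 (power model).

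**The case against.** The strongest reply is that nothing in the plan is broken. The objectives in section 2.2 ask for parameters and proportions; no trend or dose-proportionality aim is stated, and the hypothesis in section 3 concerns the MTD. Escalation rests on DLT counts. Of the safety proportions, section 8 says "the following parameters (secondary endpoints) will be used", and they are reported per cohort. Section 9.2 already plans descriptive summaries with CV, and it allows methods to be added later. The power gains depend on assumed shapes, and trend tests lose for some of them.

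Most of this stands, and it sets the priority. Two parts do not remove the point. First, the plan commits to tests at 0.05 rather than to description alone, so the choice of test is open to improvement. Second, adding a method during the analysis and explaining it in the report is transparent but is not prespecification, and in an open-label study the data will have been seen by then.

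A reader might also infer that the named tests are useless because 3 v 3 comparisons cannot go below an exact p of 2/20 = 0.10, or because large-sample Kruskal-Wallis has a true size of only 1.9% here. The documents state neither pairwise comparisons nor a large-sample reference, so neither criticism can be laid to the plan.

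**Conclusion.** The point holds as a cheap improvement. For six ordered doses, section 9.2 names only between-cohort tests that ignore order. Under assumed graded log-linear responses with 3 per cohort, trend methods have about 1.7 to 2.5 times the power of the better named test.

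Three stronger readings are not supported:
- **That trend methods roughly double power for any monotone response.** The small binary rises, the plateau and the top-dose step above contradict this, and the documents give no CV, slope or risk that would single out one scenario.
- **That a real trend is about twice as likely to be missed.** The miss ratio varies from about 1.2 to 4.4 with CV and risk.
- **That the primary PK analysis lacks power.** For exposure near dose-proportional, Kruskal-Wallis is close to certain to reject. What it lacks is an estimate: the power model gives the slope within about ±0.16 to ±0.30 (90% CI) at CV 30 to 60%.

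No dosing step, MTD rule or stated figure is affected, and no rule in the documents uses these p-values.

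**What to change.** In section 9.2, prespecify for cohorts 02 to 07:
- **Binary outcomes** (any AE, neutropenia, injection-site reactions, antibodies): per-cohort proportions with Clopper-Pearson intervals, and one exact trend test on log dose.
- **AUC and Cmax:** the power model ln(parameter) = a + b ln(dose), reporting b with its 90% CI.
- **Other ordered quantitative outcomes:** exact Jonckheere-Terpstra.
- **Any rank test:** exact or permutation p-values.
- **Support for non-monotone responses:** keep permutation Kruskal-Wallis and the per-cohort tables.
- **Status:** label all p-values exploratory.

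The cost is a few lines of text and minor programming, with no extra volunteers, visits or samples. The downsides are the loss for top-dose-only steps and rise-and-fall shapes, which is why the omnibus test stays, and the power model's log-linearity assumption, which a residual plot should check.

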2.2. Study Objectives

1. To determine the safe dose range of BCD-089, which will subsequently be used in the phase II clinical study;
2. To determine the proportion of study participants in whom a single subcutaneous administration of BCD-089 was accompanied by the development of adverse events, including the proportion of volunteers with neutropenia of varying severity;

Translated from Russian to English, dated 06-Jul-2020

3. To determine the main pharmacokinetic parameters (AUC_{0-1680} , $AUC_{0-\infty}$, C_{max} , T_{max} , $T_{1/2}$, K_{el} and CL) of BCD-089 after a single subcutaneous injection in increasing doses to healthy volunteers;
4. To determine the main pharmacodynamic parameters (C_{max} , T_{max} , C_{min} , T_{min} , AUC_{0-1680}) for C-reactive protein, IL-6 and soluble receptor IL-6;
5. To determine the proportion of volunteers, in whom binding and/or neutralizing antibodies to BCD-089 were determined following its single administration.

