4.4.1. Description of doses and dosing regimens of the study drugs

Study No. BCD-089-1 includes seven cohorts:

1. Cohort 01 - 1 volunteer to whom a single subcutaneous injection of BCD-089 at a dose of 0.06 mg/kg will be administered.
2. Cohort 02 - a maximum of 6 volunteers to whom a single subcutaneous injection of BCD-089 at a dose of 0.3 mg/kg will be administered.
3. Cohort 03 - a maximum of 6 volunteers to whom a single subcutaneous injection of BCD-089 at a dose of 0.625 mg/kg will be administered.
4. Cohort 04 - a maximum of 6 volunteers to whom a single subcutaneous injection of BCD-089 at a dose of 1.0 mg/kg will be administered.
5. Cohort 05 - a maximum of 6 volunteers to whom a single subcutaneous injection of BCD-089 at a dose of 1.6 mg/kg will be administered.
6. Cohort 06 - a maximum of 6 volunteers to whom a single subcutaneous injection of BCD-089 at a dose of 2.2 mg/kg will be administered.
7. Cohort 07 - a maximum of 6 volunteers to whom a single subcutaneous injection of BCD-089 at a dose of 2.9 mg/kg will be administered.

A guidance for preparation of the solution for injection and the table of dose calculations and administration volumes depending on the volunteer's body weight are presented in a separate manual for performing BCD-089 injections.

The inclusion of volunteers in the study is sequential. The first to participate in the study is one volunteer, representing the cohort "01", who was administered a single subcutaneous injection of BCD-089 at a dose calculated with an additional safety factor relative to the safe starting dose - 0.06 mg/kg. In the absence of grade 3-4 adverse events related to the test product, developing within the first 7 days after the injection, three volunteers are included in cohort 02. Further, the volunteer inclusion algorithm corresponds to the following general principle:

In the absence of any grade 3-4 AEs (DLT) associated with the test product within 7 days after the injection, the next cohort of three volunteers with dose escalation is included in the study - cohort 02 (cohort 03, cohort 04, etc.).

Translated from Russian to English, dated 06-Jul-2020

If grade 3-4 AEs (DLT) associated with the test product are recorded in only one volunteer in a cohort of three volunteers, three more healthy volunteers are additionally included in this cohort.

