9. STATISTICAL METHODS

9.1 Calculation of the parameters of pharmacokinetics and pharmacodynamics

9.1.1. Pharmacokinetic parameters

Based on the calculated concentration values for the anti-IL-6 monoclonal antibody in the blood of each volunteer, the following pharmacokinetic variables will be estimated at time points specified in this protocol:

1. C_{\max} - maximum serum concentration of anti-IL-6 receptor antibody over the observation period.
2. t_{\max} - time to achieve maximum serum concentration (C_{\max}) of anti-IL-6 receptor antibody.
3. AUC_{0-1680} — the area under the concentration of anti-IL-6 receptor monoclonal antibody-time curve over the time interval from 0 to 1680 hours. AUC_{0-1680} will be calculated using the trapezoid method using the following formula, where C_p is the concentration of the drug BCD-089 in the blood at the time t_p in hours:

$$t_p \in \{0; 2; 8; 12; 24; 48; 72; 96; 120; 168; 240; 336; 504; 672; 1176; 1680\}_{p=1, \dots, 16}$$

4. $AUMC_{0-1680}$ - total area under the curve of the concentration of anti-IL-6 receptor monoclonal antibody multiplied by time over the time interval from 0 to 1680 hours. $AUMC_{0-1680}$ will be calculated using the following formula:

$$AUMC_{0-1680} = \sum_{p=2}^{16} \frac{(C_p * t_p + C_{p-1} * t_{p-1}) * (t_p - t_{p-1})}{2},$$

where C_p — concentration of anti – IL – 6

– receptor monoclonal antibody против рецептора ИЛ6

Translated from Russian to English, dated 06-Jul-2020

in the blood at t_p

$$t_p \in \{0; 2; 8; 12; 24; 48; 72; 96; 120; 168; 240; 336; 504; 672; 1176; 1680\}_{p=1, \dots, 16}$$

5. **Total clearance (Cl)** is a parameter that reflects the volume of test tissue, which is cleared from the anti-IL-6 receptor monoclonal antibody per unit of time and is determined by the ratio of the anti-IL-6 receptor monoclonal antibody dose (*DOSE*) to $AUC_{(0-1680)}$:

$$CL = \frac{DOSE}{AUC_{0-1680}}$$

6. **Mean residence time (MRT)** of the anti-IL-6 receptor monoclonal antibody molecule in the body will be calculated as the ratio of $AUMC_{0-1680}$ to AUC_{0-1680} :

$$MRT = \frac{AUMC_{0-1680}}{AUC_{0-1680}}$$

7. **Elimination constant** of the anti-IL-6 receptor monoclonal antibody (k_{el}) will be determined using the following formula:

$$k_{el} = \frac{1}{MRT}$$

8. **Half-life period** of the anti-IL-6 receptor monoclonal antibody ($T_{1/2}$) will be determined using the following formula:

$$T_{1/2} = \frac{\ln(2)}{k_{el}} = \ln(2) * MRT$$

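### Section 9.2 assigns rank tests to raw AUC and concentration with no stated contrast and no dose scaling; applied across dose cohorts, they cannot show whether kinetics change with dose, and Cmax and AUC0-inf have no comparison that can

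*Combined protocol and SAP*

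**What the plan says.** Section 9.2 (Statistical analysis methods) sets the general rule: "The study results will be analyzed using the two-sided statistical hypotheses with a significance level of 0.05". It then states that "Mann-Whitney, Wilcoxon, Kruskal-Wallis, and Friedman tests will be used to compare quantitative and scaled data"; the synopsis repeats this sentence. The pharmacokinetic items listed as quantitative data include "Anti-human interleukin-6 receptor monoclonal antibody concentration", "Area under the curve", time variables such as half-life, and "Elimination characteristics (clearance, elimination constant"). Cmax is not itemised there, although the synopsis and section 7.1 make it a secondary endpoint. AUC0-1680 and AUC0-inf are the primary pharmacokinetic endpoints.

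The section does not say which groups are compared or which null hypothesis is tested. No readable text divides AUC0-inf, Cmax or concentration by dose, and none describes a dose-proportionality model. The one dose-scaled quantity is clearance, which in section 9.1.1 "is determined by the ratio of the anti-IL-6 receptor monoclonal antibody dose" to AUC0-1680.

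Objective 3 in section 2.2 is to determine the pharmacokinetic parameters "of BCD-089 after a single subcutaneous injection in increasing doses to healthy volunteers". Section 4.4.1 sets the doses: in the lowest multi-volunteer cohort "a single subcutaneous injection of BCD-089 at a dose of 0.3 mg/kg will be administered", and the highest cohort receives 2.9 mg/kg.

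**The concern.** Mann-Whitney and Kruskal-Wallis compare independent groups. The study is open-label, single-dose and non-randomised with no control arm, so dose cohort is the only evident grouping factor. If raw AUC or concentration is compared across cohorts, the null is that volunteers given 0.3 mg/kg and 2.9 mg/kg share one exposure distribution. That is not credible before the first injection.

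The useful comparative question in an escalation study is whether exposure per unit of dose stays constant. A significant raw comparison looks the same whether it does or not. A report that AUC differed significantly between doses could be taken as a change of kinetics with dose, when it shows only that the doses differed.

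**Working it through.** **Inputs from the documents.** Doses for cohorts 02 to 07: 0.3, 0.625, 1.0, 1.6, 2.2 and 2.9 mg/kg. Three mandatory volunteers per cohort, three more only after a DLT. Two-sided 0.05. The plan's only sample-size figure reproduces: 1 + 6 × 6 = 37 at most; the minimum is 1 + 6 × 3 = 19. Dose range: 2.9/0.3 = 9.67 for cohorts 02 to 07; 2.9/0.06 = 48.3 with the single sentinel volunteer.

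**Assumption.** The readable text gives no between-subject variability, so exposure is taken as log-normal with CV 20 to 100%.

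**Model.** ln(exposure) = b × ln(dose in mg/kg) + e, with e normal and SD s = √ln(1 + CV²). b = 1 is exact dose proportionality.

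**Kruskal-Wallis.** H = 12/(N(N+1)) × Σ(R_k²/n_k) − 3(N+1), with N = 18. If the cohorts separate completely, the rank sums are 6, 15, 24, 33, 42 and 51, so Σ(R_k²/3) = 6291/3 = 2097 and H = (12/342) × 2097 − 57 = 16.6. The critical value is 11.07 (chi-square, 5 df) or about 9.75 (simulated null distribution, called exact level here).

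Rejection rates under exact proportionality (b = 1), 3 per cohort:

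| CV | Raw, exact level | Raw, chi-square | Dose-normalised, exact level | Dose-normalised, chi-square |
|---|---|---|---|---|
| 20% | 100% | 100% | 5% | 2% |
| 30% | 100% | 100% | 5% | 2% |
| 40% | 99.9% | 99% | 5% | 2% |
| 50% | 99% | 95% | 5% | 2% |
| 60% | 95% | 85% | 5% | 2% |
| 80% | 79% | 60% | 5% | 2% |
| 100% | 64% | 43% | 5% | 2% |

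Simulation error and the discrete critical value move these by a point or two. With 6 per cohort, the raw chi-square rate is 100% up to CV 60% and 97% at CV 100%.

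**Can the raw test tell b = 1 from b = 1.5?** No. At b = 1.5 it also rejects in about 100% of trials at CV 30% and 50%.

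**Mann-Whitney, 3 against 3.** The smallest exact two-sided p is 2/C(6,3) = 2/20 = 0.10, so no pair of cohorts can reach 0.05, not even 0.3 against 2.9 mg/kg. With complete separation the normal approximation gives 0.081 with continuity correction and 0.0495 without, so the outcome would turn on an unstated software option.

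**What clearance already covers.** CL = DOSE/AUC0-1680 is the reciprocal of AUC0-1680 per unit dose. A reciprocal reverses the ranks, so R_k becomes n_k(N+1) − R_k and H is unchanged. Kruskal-Wallis on CL is therefore the same test as on dose-normalised AUC0-1680. Cmax, AUC0-inf and concentrations have no counterpart.

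**Power of the dose-normalised test**, 3 per cohort, exact level (chi-square in brackets):

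| CV | b = 1.3 | b = 1.5 |
|---|---|---|
| 30% | 49% (29%) | 92% (79%) |
| 40% | 30% (16%) | 72% (51%) |
| 50% | 20% (10%) | 52% (32%) |

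**Power-model slope.** The 90% half-width is t(0.95, 16) × s/√Sxx, with Sxx = 3 × Σ(ln d − mean)² = 10.73 and t = 1.746. CV 30%: 1.746 × 0.294/3.276 = 0.16. CV 50%: 1.746 × 0.472/3.276 = 0.25.

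**The case against.** Several points on the other side stand.

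- The between-cohort contrast is inferred. Section 9.2 names no groups, and Wilcoxon and Friedman suggest that some comparisons are within volunteers over time. A reader might infer that the plan states a between-cohort test of raw AUC and Cmax; it does not. What is certain is that contrast and scaling are unspecified.
- A reader might infer that every listed test rejects almost surely. Exact Mann-Whitney at the mandatory cohort size cannot reject at all, and Kruskal-Wallis falls to about 60 to 80% at CV 80%.
- A reader might infer that the pharmacokinetic testing is wholly uninformative. Clearance, elimination constant and half-life have a meaningful equality null under linear kinetics, and clearance covers AUC0-1680.
- No visible decision uses a pharmacokinetic p-value. Escalation depends on DLTs, the only stated hypothesis (section 3) concerns the maximum tolerated dose, and analysis follows the last volunteer's data.
- Dose-normalised Kruskal-Wallis is weak against moderate departures, as the table shows.

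One argument carries little weight. The plan allows its list of methods to be extended, but that names no method and does not withdraw the raw tests. A proportionality analysis chosen after seeing the data is also weaker than a prespecified one.

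**Conclusion.** The concern holds in a limited form. On the natural reading, Kruskal-Wallis on raw exposure across cohorts 02 to 07 rejects in about 95 to 100% of trials at exact level (about 85 to 100% by chi-square) under exact proportionality, for CV 30 to 60% and 3 per cohort. Exact pairwise Mann-Whitney never rejects. Neither outcome says whether kinetics change with dose. The real gap is Cmax, AUC0-inf and concentrations, since clearance serves AUC0-1680.

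This rests on the inferred contrast, log-normal exposure and an assumed CV. It affects how the pharmacokinetic results are interpreted. The documents do not support a reading that safety or escalation is affected.

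**What to change.** In section 9.2 (Statistical analysis methods):

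1. Describe raw AUC, Cmax and concentrations by cohort, without between-cohort tests.
2. Compare dose-normalised Cmax, AUC0-inf and concentrations across cohorts, with CL serving for AUC0-1680.
3. State whether the divisor is mg or mg/kg. If exposure follows mg/kg, dividing by mg adds weight noise: with an assumed 15% SD in body weight, power at exponent 1.5 and CV 30% falls from about 92% to 85%.
4. Report as the main estimate the power-model slope of log exposure on log dose, with its confidence interval.
5. State that failing to reject does not establish proportionality, given the low power at these cohort sizes.

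The cost is a few sentences and a little more analysis. Each volunteer's dose in mg is already calculated from body weight, so no new data are needed. The slope interval will be wide, about ±0.16 to ±0.25 at 90% for CV 30 to 50%, but it shows openly how little 18 volunteers can settle.

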4.6.3.12. Assessment of injection site reactions

Injection site reactions are recorded in a separate Injection Site Reaction Registration Form (see Appendix 1). If several injections have been performed, each injection site should be evaluated separately.

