8.4.1 AE/SAE registration

Presence or absence of adverse events during the period from the last visit is evaluated at each visit. Any serious adverse event observed in a volunteer from signing the informed consent form should be registered in source documents and in the dedicated Adverse Event Reporting Form (in eCRF).

Adverse events are registered and numbered consecutively, as they occur. Each AE is reported using the AE Reporting Form. The rules for AE/SAE reporting are described in detail in the Guidance provided by the Sponsor.

Adverse events are registered regardless of seriousness or causal relationship with study therapy. **All AEs are subject to recording in the study, including Grade 1 AEs (CTCAE v.4.03).** If the same adverse event reoccurs (after the previous case resolved), it should be registered as a new adverse event, with a separate number.

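### Section 9.2 defines a receptor-occupancy variable per sample and names only tests that need independent units; the volunteer should be the unit of any test (low severity, exploratory measure)

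*Combined protocol and SAP*

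**What the plan says.** Section 9.2 (Statistical analysis methods) plans "two-sided statistical hypotheses with a significance level of 0.05". For categorical variables it says: "The categorical data will be processed using the Fisher's exact test and the" Pearson chi-square test. The list of categorical variables opens with "Proportion of samples showing the maximum signal for membrane IL-6 receptor occupancy". The same list counts neutropenia by subjects, so the unit changes within one list. Percent occupancy appears separately under quantitative data. The Mann-Whitney, Wilcoxon, Kruskal-Wallis and Friedman tests are named for quantitative and scaled data only.

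The synopsis and sections 4.1.2 and 7.2 give occupancy at four post-dose times: 2, 168, 336 and 504 h. All three say that it is not a study endpoint; sections 4.1.2 and 7.2 also call it pilot work.

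On safety, section 9.2 lists "Frequency of injection-site reactions (total and depending on the type of the lesion" and frequencies of AEs without giving a unit. Section 8 is explicit about its unit: "Proportion of subjects who developed injection site reactions in each cohort". At data capture, section 4.6.3.12 says "If several injections have been performed, each injection site should be evaluated separately", and section 8.4.1 says "If the same adverse event reoccurs (after the previous case resolved), it should be registered as a new adverse event".

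**The concern.** Fisher's exact and Pearson chi-square tests assume that every entry in the table is an independent unit. Samples from one volunteer are likely to resemble each other. If samples are the unit and all times are pooled, a three-volunteer cohort contributes 12 entries from 3 independent people, and the p-value is too small. Ordinary variation between volunteers could then be reported as a dose difference in receptor occupancy.

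The frequency items for safety raise a milder question. Recurrent events and separate injection sites are recorded individually, and section 9.2 does not repeat that these items are to be counted per subject.

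**Working it through.** **Inputs from the documents.** Two-sided alpha 0.05; tests Fisher and Pearson chi-square (section 9.2). Four named post-dose occupancy times (synopsis, 4.1.2, 7.2). Cohorts 02–07 have 3 volunteers each, up to 6 after a DLT (sample-size table). The plan states no error rate for these tests. Its only calculated figure is the sample size, which reproduces: 1 + 6 × (3 + 3) = 37 at most, and 1 + 6 × 3 = 19 mandatory.

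**Inputs assumed.** The ICC (ρ), the probability p that a sample shows the maximum signal, pooling over the four times, and no true difference between cohorts.

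**Rough size of the problem.** Per cohort there are 3 × 4 = 12 samples. The design effect is 1 + (4 − 1)ρ, and the effective number of samples is 12 divided by it:
- ρ = 0.1: 12 / 1.3 = 9.2
- ρ = 0.3: 12 / 1.9 = 6.3
- ρ = 0.8: 12 / 3.4 = 3.5

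**False-positive rates.** Each volunteer's probability is drawn from a Beta distribution with parameters p(1 − ρ)/ρ and (1 − p)(1 − ρ)/ρ. His four samples are then binomial with that probability. Samples are pooled in each of two cohorts and tested at p ≤ 0.05. The ranges cover p from 0.2 to 0.8 and cohorts of 3 or 6 volunteers. They come from simulation with 20,000 replicates per setting, and exact enumeration of the same model agrees to within about one percentage point.

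| ICC (assumed) | Fisher | Chi-square, uncorrected |
|---|---|---|
| 0 | 1.2–3.0% | 3.9–6.8% |
| 0.1 | 2.6–5.8% | 6.9–10.5% |
| 0.3 | 6.7–11.8% | 13.5–19.0% |
| 0.5 | 11.3–17.9% | 21.2–26.3% |
| 0.8 | 14.1–26.3% | 31.7–37.4% |

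**Sensitivity to the assumptions.**
- *Steep decline over time.* With probabilities 0.95, 0.8, 0.4 and 0.1 at the four times and a latent correlation up to 0.9, Fisher stays below 3% and chi-square reaches only about 6%.
- *Moderate decline.* With 0.8, 0.7, 0.5 and 0.4 and a latent correlation of 0.5, Fisher gives 8–10% and chi-square about 15%.
- *Two time points compared in the same volunteers.* The error goes the other way. With 18 volunteers and a latent correlation of 0.5, Fisher gives 0.8% and chi-square 2.3%.
- *One time point, two cohorts.* There is one sample per volunteer, so the rate no longer depends on the ICC. Fisher on 3 v 3 never rejects, because its smallest two-sided p-value is 2 / C(6,3) = 2 / 20 = 0.10.

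**The case against.** The strongest reply is that pooling is inferred. Section 9.2 does not say that samples are combined over time, or which groups are compared. Occupancy is defined time point by time point, and at one time point sample and volunteer coincide, so both tests have independent units. The occupancy assay section and the contents of its sampling table are blacked out, so a rule for summarising samples may exist there. Percent occupancy is already listed as quantitative with suitable tests. The plan also allows methods to be added. All of this stands, and it makes the inflation conditional. It does not remove the defect in the visible text: the variable is defined per sample, the tests named for it need independent units, and permission to add methods fixes no unit.

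Three stronger readings are tempting and not supported:
- *The plan will double-count adverse events and injection sites.* Separate recording is data capture, not an analysis rule, and the safety endpoints in sections 4.1.4 and 8 are per subject. The plan also uses frequency for early discontinuation, which happens once per person. This is an ambiguity, and the error rates above do not apply to it.
- *Pain scores are affected too.* They are listed as quantitative and never go to these tests.
- *The test is wrong by a known amount.* The ICC and the time course of occupancy are not in the documents.

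**Conclusion.** The point holds in a limited form. As worded, the occupancy item invites a test that treats repeated samples from one volunteer as independent. For a pooled comparison of two cohorts, the false-positive rate would pass the nominal 5% clearly at an ICC of about 0.3 or more. At ICC 0.1 only chi-square exceeds it throughout the range. These figures rest on pooling over time, a roughly constant probability of 20–80% and an assumed ICC. They shrink to near nominal if occupancy falls steeply, and the clustering problem disappears if times are tested separately.

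Severity is low. Occupancy is not an endpoint, and dose escalation follows DLTs per volunteer rather than these p-values. The safety part is a request for clarification only.

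**What to change.** In section 9.2, make the volunteer the unit of any test of receptor occupancy. Compare cohorts at each time point with one value per volunteer, using the percent occupancy already listed as quantitative. Report any proportion of samples pooled over time descriptively, without a test.

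For consistency, word the frequency items for safety as numbers of volunteers, to match the per-subject endpoints in sections 4.1.4 and 8. Event and site counts can still be listed.

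The cost is wording only; no visit, sample or procedure changes. The downside is a smaller apparent sample and larger p-values. Between two three-volunteer cohorts, for example, a Fisher test with one binary value per volunteer cannot go below 0.10. That reflects the information that three volunteers per cohort provide.
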